Target Population	
Inclusion Criteria
 
1. Age from 18 months to 70 years.2. Suppression of consciousness related to a neurological injury..3. GCS less than 13.4. Acute brain Injury by TBI, hypoxic-ischemic Insult, cardiac arrest, or Stroke.5. 2 to 90 days from MSABI to enrollment.6. Have a routine clinical care surface EEG performed after the admission to PICU, NSICU, SICU, CTICU, CICU or MICU.7. Hospitalized at PICU, NSICU, SICU, CTICU, CICU or MICU 
Exclusion Criteria
 
1. Previous medical history of Epilepsy.2. Previous medical history of neurological conditions that lead to dependence greater than expected for age on care for basic daily activities given by Barthel Index score (BIS) less than 80.3. Brain death.4. Currently able to speak fluently.5. Currently at one's prior reported baseline mental status.6. Known allergy/Hypersensitivity or medical contraindications (like porphyria or cardiac arrhythmias) to the treatment protocol options, leaving no potential combination of drugs for the intervention without concerns for adverse events related to known preexistent conditions..7. Prisoner human subjects by medical chart review.8. Pregnant.9. Treating physician determines the patient is no candidate to receive 2 of the 5 protocol-specified ASM.

	10. Contraindications for MRI scan.
Numbers of Enrollees	
Up to 68 individuals will be screened with the goal of enrolling 54 eligible individuals and identifying a subset of 22 participants who are SzNET positive (see Study Schema, Figure 2). Using a quota sampling strategy, 11 SzNET+ patients will be recruited consecutively for each EEG+ and EEG- strata to ensure the necessary number of patients for the interventional phase of the study.

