Safety Monitoring		Any time (AT) After E		
Adverse event related with the transportation to the MRI scan.	Ordinal 1-5	AT after E	-	safety monitoring
Adverse event related with the transportation to the MRI scan. Description	nominal	AT after E	-	safety monitoring
Adverse event related with the intervention	Ordinal 1-5	AT after E	-	safety monitoring
Adverse event related with the intervention. Description	nominal	AT after E	-	safety monitoring
Dropout	binary	AT after E	Aim 6	Secondary outcome
Dropout date	ordinal	AT after E	Aim 6	Secondary outcome
Dropout cause	nominal	AT after E	-	safety monitoring
Feasibility				
Informed consent acceptance	Binary	E	Aim 6	confounder

¹ Units of measurement or the scale.

² Occasions of evaluation or retrieval: **S** = screening, **E** = enrollment, **2** = rs-fMRI#2, **3** = 3 months

³ The specific aims in which the variable will play a role in data analyses.

⁴ will be collected by one of the NSICU Post-Discharge clinics.

In Table 2, the treatment regimens must include two from:

6. Phenobarbital
7. Levetiracetam
8. Lacosamide
9. Valproate
10. Fosphenyton

In Table 1, the allowed Presumed etiologies of disorder of consciousness are:

1. Hypoxia/anoxia (i.e., respiratory arrest with preserved circulation)
2. Hypoxic-ischemic injury (i.e., cardiac arrest).
3. Ischemic stroke.
4. Intracerebral hemorrhage.
5. Subarachnoid hemorrhage.
6. Subdural hemorrhage
7. Epidural hemorrhage
8. Traumatic brain injury (penetrating).
9. Traumatic brain injury (non-penetrating).
10. Venous sinus thrombosis/cortical vein thrombosis

Baseline Variables:

- The Medical record domain variables will focus on retrieving information to screen patients and verify inclusion-exclusion criteria. Thus, the previous history of epilepsy and neurological problems that could lead to functional dependence greater than expected for age are relevant confounders that will be avoided in this pilot trial. The presumed etiology of DoC are the inclusion criteria, and we expect to evaluate the rs-fMRI for exploratory purposes in subgroup analysis. Glasgow coma scale GCS is a baseline variable that will be collected in more time points.

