5.2.1. Inclusion Criteria

[figure not shown]

Fig. 1. Adult and Peds SABI EEG and Seizure Network (SN) prevalence (N=63). EEG-SN+ comprise 30% of the SABI population.

In order to be eligible to participate in this study, an individual must meet all of the following criteria:

- Age from 18 months to 70 years at ICU admission by medical chart review.
- Suppression of consciousness related to a neurological injury by medical chart review.
- GCS less than 13 at enrollment.
- Diagnosis of Acute brain injury by TBI, hypoxic-ischemic insult, cardiac arrest or stroke by medical chart review.
- 2 to 90 days from acute brain injury to enrollment time by medical chart review.
- Have a routine clinical surface EEG performed after the admission to PICU, NSICU, SICU, CTICU, CICU or MICU.
- Clinically stable to undergo MRI scan, This stability is defined by care team concept, which should be stated in the medical records.
- Hospitalized in NSICU, PICU, SICU, CTICU, CICU or MICU

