5.2.2. Exclusion Criteria

Any individual who meets one or more of the following criteria will be excluded from participation:

- Previous medical history of Epilepsy by medical chart review.
- Previous medical history of neurological conditions that lead to dependence on care for basic daily activities, by BIS less than 80, examined with the patient's LAR at the time of the in person interview for obtaining the informed consent. If there is medical history of neurological conditions with concerning for impaired independence and the functional status of the patient cannot be addressed properly the patient will be excluded from participation.
- Known allergy/Hypersensitivity or medical contraindications (like porphyria or cardiac arrhythmias) to the treatment protocol options, leaving no potential combination of drugs for the intervention without concerns for adverse events related to known preexistent conditions.
- Considered with Brain death by the care team in the medical record, at any time.
- Is following Commands in 3 different exams from at least 2 different providers.
- Contraindications for MRI scan.
- Prisoner human subjects by medical chart review.
- Confirmed currently pregnant by medical history or by positive blood or urine pregnancy test done in the present hospital admission.
- Treating physician determines the patient is no candidate to receive 2 of the 5 protocol-specified ASM.

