The screening will involve the in-person interview time period because the Barthel Index score is an additional test required to determine study eligibility. Thus, screening and enrollment will be performed on the same day, which is essential to reduce drop out during the screening period because the clinical state of these patients varies day by day. This strategy is also designed to reduce the anxiety of the families/LAR. The time frame to schedule the screening/enrollment interview after the phone call is flexible only to the extent that it must still meet the max 90 days enrollment deadline from MSABI. That means the available time to schedule the interview depends on the time since MSABI started, to meet the eligibility criteria. On the day of the telephonically scheduled interview with the LAR, the eligibility criteria by medical chart review will be double checked before the interview. If the patient is still eligible, the meeting will proceed. After presenting the study and its purpose, the study personnel will complete the Barthel Index (see appendix A) with the help of the LAR. If the score does not exclude the patient, the interviewer will explain potential risks and benefits and ask for consent for the study.

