7.3. Enrollment

Once informed consent is obtained and the patient is enrolled, the coordinator will double-check previous history of porphyria, allergies, and hypersensitivity to the potential ASM listed in the study to provide a list of the treatment protocols that could be used for the patient if allocated to intervention. On the same day, the study coordinator will schedule the rs-fMRI for the following days and inform the research and the care teams of the scheduled date. This date should be within three days at maximum, and the intervention allocation must be done within six days from enrollment. Considering those dates, the minimum and maximum times from MSABI to the first rs-fMRI are 4, and 48 days correspondingly. The minimum and maximum times from MSABI to the intervention are 5 and 51 days, correspondingly. The family will be told that all the rs-fMRI results will be provided and explained after the follow-up research tests, and no further instructions are needed.

Screening/enrollment interview Activities (Day 0)

- BIS assessment for score (>80) through interview with potential LAR.
- Written Informed Consent Obtained from LAR.

- Consent must be obtained within 90 days from the participant's MSABI.
- Confirming baseline variables are collected through medical chart review.
 - Supratentorial decompressive craniectomy, current GCS score, presence of spontaneous ventilation.
- Verify with the LAR about: porphyria, co-morbidities, medical implants or contraindications for MRI, allergies, and hypersensitivity to the potential ASM.
- Provide a list of the treatment ASMs recommended for this participant that could be used if allocated to intervention.
- Notify Clinical Team about participant enrollment.
 - Verify with study team about which 2 combined ASMs could be administered in case of allocation to treatment.
 1. Phenobarbital 20 mg/kg loading dose
 2. Levetiracetam 60mg/kg loading dose
 3. Lacosamide 10 mg/kg loading dose
 4. Valproate 30 mg/kg loading dose
 5. Fosphenyton 20 mg/kg loading dose

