13.1.2. Consent Procedures and Documentation

Informed consent is a process that is initiated prior to the individual's or their LAR's agreeing to participate in the study and continues throughout the individual's study participation.

The first approach to the patient's LAR will be by telephone, presenting the researcher as non-care team personnel, part of a research team from the neurology department, and explaining the purpose of the call with a general idea of the study; then will ask for consent to schedule a personal interview to give further details of the study and the screening procedures. If the LAR accepts, an interview will be scheduled soon, in English or Spanish, according to the LAR preferences. The interview can be performed by one of the study investigators or by the research coordinator who will be trained to perform this activity.

At the interview, the screening process and the Barthel Index will be explained, if the LAR agree to continue the screening, the Barthel Index will be completed. For patients with a Barthel score of 75 or less the researcher will explain that the patient is not eligible for the study, in the case of a Barthel score of 80 or more the researcher will continue with the informed consent process to enroll the patient.

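### The consent interview turns patients away on the raw Barthel score, although the exclusion criteria use that score only for prior neurological conditions

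*Combined protocol and SAP*

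**What the plan says.** The Barthel exclusion appears in several places, with different conditions attached.

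- **Section 1 (synopsis), exclusion 2:** "Previous medical history of neurological conditions that lead to dependence greater than expected for age on care for basic daily activities", measured by a Barthel score below 80.
- **Section 4.3 (baseline variables)** repeats that purpose: "neurological problems that could lead to functional dependence greater than expected for age are relevant confounders", to be kept out of this pilot.
- **Section 5.2.2** keeps the neurological history but not the age qualifier: "Previous medical history of neurological conditions that lead to dependence on care for basic daily activities, by BIS less than 80". It adds that the score is taken with the legally authorized representative at the in-person interview.
- **Section 7.2** is neutral on conditions: "If the score does not exclude the patient, the interviewer will explain potential risks and benefits and ask for consent for the study".
- **Section 7.3 (activity list for day 0):** "BIS assessment for score (>80) through interview with potential LAR".
- **Section 13.1.2** states both branches of the interview decision without conditions: "For patients with a Barthel score of 75 or less the researcher will explain that the patient is not eligible for the study", and "in the case of a Barthel score of 80 or more the researcher will continue with the informed consent process to enroll the patient".

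The age criterion in section 5.2.1 is "Age from 18 months to 70 years at ICU admission by medical chart review". Section 5.3.2 makes the Barthel Index the sole screening test and bars re-screening of anyone found ineligible at the interview. The variable table in section 4.3 lists one pre-injury Barthel score on a 0-100 scale and names no age-adjusted form. Appendix A, which holds the index, is not in the text available here.

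**The concern.** The interview is where eligibility is settled. If the rule used there is broader than the exclusion criterion, patients whom the protocol means to admit are refused, and two members of staff working from different sections can decide the same patient differently.

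The Barthel Index scores independence in basic daily activities. A previously healthy child near the lower age limit depends on others for such activities because of age, and the synopsis wording appears designed to allow for this. A raw cut-off does not. The same applies to an older patient whose dependence has a non-neurological cause.

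At stake are avoidable screen failures that cannot be reversed, and a sample that may under-represent part of the stated age range. The amendment log gives a higher enrolment rate as the reason for the present age range, and a raw cut-off works against that reason at the youngest ages.

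**Working it through.** This is a question of eligibility logic, so the main check applies each rule to the same patients.

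**1. The rules**

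- Synopsis: exclude if there is a previous neurological condition, dependence beyond that expected for age, and a score below 80.
- 5.2.2: exclude if there is a previous neurological condition causing dependence, and a score below 80.
- 13.1.2: exclude if the score is 75 or less; proceed if it is 80 or more.
- 7.3: proceed only if the score is above 80.

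**2. The rules applied**

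| Patient | Synopsis | 5.2.2 | 13.1.2 | 7.3 |
|---|---|---|---|---|
| A. No neurological history, dependence normal for age, score 75 or less | kept | kept | turned away | turned away |
| B. No neurological history, dependence from a non-neurological cause, score 75 or less | kept | kept | turned away | turned away |
| C. Neurological history, dependence normal for age, score 75 or less | kept | excluded | turned away | turned away |
| D. Neurological history, dependence beyond age, score 75 or less | excluded | excluded | turned away | turned away |
| E. Score exactly 80, any history | kept | kept | proceeds | does not pass |

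Rows A and B are the contradiction: both formal lists keep the patient and both operational passages refuse the patient. Only row D gives one answer throughout. Row C shows the effect of the age qualifier missing from 5.2.2. Row E is a smaller mismatch, confined to the strict inequality in 7.3.

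**3. The planning figures that depend on the Barthel rule**

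Section 5.1 reproduces from its own inputs:

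- EEG-negative: 11 / 0.30 = 36.7, so 37.
- EEG-positive: 11 / 0.67 = 16.4, so 17.
- Enrolled: 37 + 17 = 54, as stated.
- Screened: 54 / 0.80 = 67.5, so 68, as stated. By stratum, 37 / 0.80 = 46.25 (stated 46) and 17 / 0.80 = 21.25 (stated 22).

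The 80% eligible share is attributed partly to the Barthel requirement, but the plan does not say which version of the rule it assumes.

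**4. What an extra loss would cost**

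Let t be the share of otherwise eligible patients refused only because of dependence normal for age. The documents give no value for t. If the loss comes on top of the planned 20%, the number to screen is 54 / (0.80 x (1 - t)):

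- t = 0: 67.5, so 68.
- t = 5%: 71.05, so 72.
- t = 10%: 75.
- t = 20%: 84.4, so 85.

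This converts an assumed t into a screening number. It does not estimate t.

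**The case against.** The strongest reply is that 13.1.2 is shorthand. Section 5.2.2 places the Barthel assessment at the same interview, section 7.2 has the chart criteria double-checked just before it, and the entry in 7.3 is only a bullet in an activity list. Staff would then know the patient's neurological history and could apply the full criterion. On that view no eligible child is lost, and the formal criteria govern.

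Part of this stands. The formal criteria do not exclude a healthy toddler, so the defect is a conflict between passages and not a decision to exclude such children. The shorthand reading does not remove the conflict. Section 13.1.2 states a definite outcome to be told to the representative, allows a trained coordinator to conduct the interview, and does not refer back to the history condition.

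A second reply is that the synopsis may treat a score below 80 as the measure of excess dependence, not as a separate condition. That reading would change row C in the table. Rows A and B are unaffected, because the synopsis and 5.2.2 still require a neurological history.

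A third reply is that section 5.1 already allows for 20% ineligibility, partly for the Barthel score. This is fair, and it is one reason why the net loss cannot be stated.

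A reader might also infer that almost all children up to some age are rejected, that the lowered age limit is largely cancelled, or that no aim covers the stated population. The documents do not support these readings:

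- They contain no Barthel scores by age, no age distribution of candidates, and no age at which a raw cut-off would stop mattering.
- The present age range also has an upper limit of 70 years, which the argument about toddlers does not touch.
- The 109 paediatric ICU patients per year in section 5.2 are counted by diagnosis code, before the GCS, EEG, MRI-stability and consent filters. A share of them cannot be set against 54 enrolled.

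**Conclusion.** The contradiction holds. Sections 13.1.2 and 7.3 decide on the score alone, whereas the synopsis and 5.2.2 do not exclude a patient without a previous neurological condition, whatever the score. Such a patient scoring 75 or less is eligible under the formal criteria and is refused, with no second chance, under the interview rule. This follows from the text and needs no numerical assumption.

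That the youngest children are the main group affected is plausible but is an inference from what the index measures and from the synopsis's reference to age. The size of the enrolment loss cannot be derived from the documents. The point merits correction because the rule as written gives a result that the eligibility criteria do not intend, and correcting it is nearly free. It does not by itself invalidate any of the aims.

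**What to change.** Reconcile the passages so that one criterion applies everywhere.

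- In 13.1.2 and 7.3, replace the bare cut-offs with the exclusion as defined: a score below 80 excludes only when a previous neurological condition causes dependence beyond that expected for the patient's age. This also settles the score of exactly 80 in 7.3.
- In 5.2.2, add the age qualifier that the synopsis and section 4.3 already carry.

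The change needs no new data and leaves the sample-size figures as they are. Its one cost is that the interviewer must judge what is expected for age in young children, which the synopsis already implies.

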13.2. Study Discontinuation and Closure

This study may be temporarily suspended or prematurely terminated if defined stopping rules are met. Written notification, documenting the reason for study suspension or termination, will be provided by the suspending or terminating party to the study participant's LAR, the Neurology Department and the IRB.

If the study is prematurely terminated or suspended, the Principal Investigator (PI) will promptly inform study participants, the Institutional Review Board (IRB), and Neurology department and will provide the reason(s) for the termination or suspension. Active study participants or their LAR will be contacted and informed of changes to the study.

Examples of circumstances that may warrant termination or suspension of the study include:

- Criteria established in the Master protocol document (MPD) for early termination of the study have been satisfied
- Detection of an unexpected unacceptable level of risk to participants
- Futility due to insufficient adherence to protocol requirements.
- Unexpected inability to recruit participants.

The study may resume once concerns about safety, protocol compliance, and data quality are addressed, and meets the requirements of the UNC Neurology department and the IRB.

13.3. Confidentiality and Privacy

Participant confidentiality and privacy is strictly held in trust by the UNC Clinical Resting State fMRI Service, the PICU, the NSICU, the SICU, the CICU, the CTICU, the MICU, and the Neurology Department. This confidentiality is extended to cover EEG recordings and rs-fMRI data in addition to the clinical information relating to participants. Therefore, the study protocol, documentation, data, and all other information generated will be held in strict confidence. No information concerning the study or the data will be released to any unauthorized third party without prior written approval of UNC.

All research activities will be conducted in as private a setting as possible.

The Neurology Department and representatives of the Institutional Review Board (IRB) may inspect all documents and records required to be maintained by the investigator, including but not limited to, medical records (office, clinic, or hospital) and pharmacy records for the participants in this study. The clinical study site will permit access to such records.

The study participant's contact information will be securely stored at UNC Health information system site for internal use during the study. At the end of the study, all records will continue to be kept in a secure location for as long a period as dictated by the reviewing IRB and the Institutional policies requirements.

Study participant research data, which is for purposes of statistical analysis and scientific reporting, will be transmitted to and stored at the PI's UNC OneDrive account. This will not include the participant's contact or identifying information. Rather, individual participants and their research data will be identified by a unique study identification number. The study data entry and study management systems used by clinical site and by the UNC clinical resting state fMRI service research staff will be secured and password protected. At the end of the study, all study databases will be de-identified and archived in SOM Dept of Neurology Protected Research Database.

13.3.1. Certificate of Confidentiality

Not Apply.

13.4. Future Use of Stored Specimens and Data

Data collected for this study will be analyzed and stored at the PI's UNC OneDrive and The School of Medicine drive. After the study is completed, the de-identified, archived data will be transmitted to and stored at a private folder for the UNC Clinical resting State fMRI Service in the official School of Medicine drive, for use by other researchers including those outside of the study.

Permission to transmit data to the School of Medicine drive should be included in the informed consent. With the participant's approval and as approved by local Institutional Review Boards (IRBs), de-identified biological data will be stored at the School of Medicine drive. The files at the School of Medicine drive will also be provided with a code-link that will allow linking the biological recordings (MRI imaging and EEG recordings) with the phenotypic data from each participant, maintaining the blinding of the identity of the participant. The blood samples collected for medication serum levels will not be stored, the results will be used just for treatment-dose adjustment purposes and not collected as research variables. This phenobarbital serum level information will be stored and managed in the same fashion as the patient's clinical information.

